٦	ehydration			
	Sunken eyes	present / absent		
	Capillary refill time	Seconds (delayed = more than 3 seconds)		
	Skin turgor/elasticity	Time in seconds to return to normal graded: immediate,		
		slow, very slow (>2sec)		
М	Malnutrition			
	Height/length	continuous scale		
	Admission weight	continuous scale		
	Pedal edema	present / absent		
Sh	nock			
5/1	Heart rate	continuous scale		
	Oxygen saturation	continuous scale (oximetry), adjusted for altitude		
	Miscellaneous			
		procent (abcont		
	Jaundice	present / absent		
	Bulging Fontanelle (< 18 months of age)	present / absent		
	Rash	Type: petechial, purpural, measles		
La	boratory			
	Complete Blood Count, including the following:			
	Hemoglobin	continuous scale		
	Peripheral white cell count	continuous scale		
	Differential white cell count	Percentage		
	Platelet count	continuous scale		
	Malaria	rapid test or smears		

Ta	able IV. List of symptoms, signs and laboratory tests that may be evaluated at admission		
	Variable	Notes	
	HIV serology	PCR confirmation in children under 18m; parent may decline HIV testing	
	Sickle Cell Testing	in some African sites only, method may vary by site (PCR, HPLC or gel electrophoresis)	
	Thalassemia	In Thailand only	

Two PERCH sites, South Africa and Zambia, will also initiate voluntary HIV testing for the mothers of PERCH cases. Currently at both sites HIV testing is done routinely as part of antenatal care. These results may be recorded as exposure to HIV on a child's health card ('Road to Health Card' in South Africa and 'Under 5 Care' in Zambia), but are not captured as part of a child's record in PERCH. We propose either asking the mother for documentation of her recent HIV test result or offering her testing if she has not been tested recently. All testing will be done using trained nurses or HIV testing counselors. We will ask for consent to link these results with the child's PERCH data. We believe that knowing the mother's HIV status will be critical in evaluating a child's HIV exposure status at the time of enrollment in to PERCH. It has been shown that, even in the absence of HIV infection in an infant, HIV exposure during the pregnancy and peripartum period can lead to increased risk of severe or very severe pneumonia; we would like to evaluate this risk further.

The counseling and testing process will follow local ethics requirements, and the timing of the consent for a mother's HIV test will be done according to the clinic flow at each site.

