*at least one specimen. Delay collection of induced sputum from those with bronchospasm and severe hypoxia until clinical conditions permit

**in settings with a history of use and where possible; not recommended in areas with HIV+ infants

***volume may vary by site (i.e. in sites where more blood is collected as standard of care – up
to 7.5 mL without weight –based adjustments)

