4.5.1.5 Induced sputum

Induced sputum will be collected from all cases except those with contraindications, which include the following: severe hypoxia (<92% on supplemental oxygen), inability to protect airways, severe bronchospasm at admission, seizure within the past 24 hours, or deemed inappropriate by a study clinician for another reason (e.g. mid-face trauma, inhalational injury, pulmonary edema, congestive heart failure, congenital heart disease, etc). If the above symptoms resolve during hospital course, induced sputum collection may be reconsidered at that point.

The following guidelines will be utilized for the collection of induced sputum.

- Sites will use Metered Dose Inhalers (MDIs) for bronchodilation
- Sites will employ light chest percussion in children < 2 years to improve mobilization of sputum. In children > 2 years, their cough reflex should be sufficient to mobilize sputum after induction with nebulization of hypertonic saline
- The specimen should optimally be collected within 24 hours. After 24 hours, induced sputum can still be collected (to test for tuberculosis and *Pneumocystis jiroveci*), but bacteriology should not be performed unless antibiotic therapy fails.
- The quantity of the specimen should be at least 1 mL.
- The quality of the specimen will be assessed using the "Bartlett's Score". Specimens with suboptimal Bartlett's Score will still be processed by the lab for all specified testing, but the Bartlett Score and consequent microbiology results will be considered in the analysis. Suboptimal Bartlett Scores will also be reported to the clinical team doing the procedure as a performance indicator.
- Some sites will perform a second induced sputum to improve the diagnostic yield for tuberculosis, as has been shown in other studies (Zar et al. 2005). This will be stipulated in site specific appendices.

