- Lung aspiration will only be performed in patients with large peripheral consolidation on chest-xray, distant from great vessels, such that the risk of failing to get a specimen and the risk of inducing haemorrhage are both minimal. Cases with conditions that pre-dispose to complications (i.e. coagulopathy, suspected PCP, chest hyper-expansion, chest cysts or bullae) will be excluded from having this procedure performed. Cases with contraindications including the following will be excluded from lung aspirate specimen collection: presence of pneumatocoeles on CXR, post-measles pneumonia, patient is clinically unstable as determined by a clinician, CPR performed within the last 24 hours.
- Patients will be followed up closely for the 4 hours after the procedure and will be investigated with a chest radiograph if they show signs of clinical deterioration based on the clinical judgment of the physician.
- Performance of chest radiograph will be used to localize the consolidation. Following the procedure CXR will be repeated if clinically indicated. This is rarely needed but will be available at all sites.
- Specimens from lung aspirates will be tested in real time for the microbiologic cause of the pneumonia episode using all assays available at the site. This policy will maximize the opportunity for the subject to derive immediate clinical benefit from the procedure. The principal benefit to children undergoing the procedure is the early (and potentially life-saving) identification of pathogens that are not adequately treated with first line antimicrobial therapy. In developing country settings, using WHO treatment guidelines, these pathogens include *S. aureus*, most pathogenic gram-negative bacilli and tuberculosis. Without accurate diagnosis many of these children will be inadequately treated and a significant proportion will go on to chronic disease (in the case of TB) or death.

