5.2 Induced sputum

Induced sputum is preceded by bronchodilator and then hypertonic saline inhalation to loosen up lower respiratory tract secretions, and induced by chest percussion and cough. The induced sputum that is coughed into the posterior pharynx is aspirated using suction. This procedure confers a mild increase over minimal risk because of the use of inhaled hypertonic saline that may, in theory, induce some airway hyper-reactivity. The child may also require an increase in their oxygen requirement for minutes to hours if the mobilized secretions cause some temporary reduction in the ventilation of lung sub-segments, or if the procedure induces some transient bronchospasm as described here. For the PERCH study, the agreed upon contraindications for the induced sputum procedure are oxygen saturation of less than 92% on oxygen, inability to protect airways, severe bronchospasm at admission, seizure within the past 24 hours, or deemed inappropriate by a study clinician for another reason (e.g. mid-face trauma, inhalational injury, pulmonary edema, congestive heart failure, congenital heart disease etc.) . If these conditions resolve during hospital course, an induced sputum can be considered at that point.

The sputum induction procedure itself can benefit the child because the inhaled bronchodilator may be therapeutic for a child with severe or very severe pneumonia as can the chest physiotherapy to assist in clearing secretions. The bacterial and M. tuberculosis results from the induced sputum can also provide benefit to the child to target or modify therapy if clinically indicated in relation to the sputum results. While induced sputum is rarely *collected* in the course of routine clinical care from children for diagnostic purposes, the *procedure* to obtain this specimen ("chest physical therapy with acceleration of the expiratory flow") is done routinely to relieve difficulty breathing in hospitalized children in France and New Caledonia, and has also been shown to be of minimal risk in the absence of specific contra-indications such as neurologic disease compromising the airway, broken ribs, osteogenesis imperfect, significant thrombocytopenia (personal communication: Pr. [name], Hopital Antoine Béclère, Clamart, France).

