5.7 Serious Adverse Events

5.7.1 Serious Adverse Event definition:

Among children who had a lung aspirate:

- Death during hospitalization
- Pneumothorax or significant haemoptysis (>5 mLs) at any time following the procedure, during the hospitalization
- Clinical deterioration within 4 hours following the lung aspirate procedure defined as:
 - Drop in oxygen saturation below 92%, resulting in increased supply of supplemental oxygen for 10 minutes or more
 - Deterioration in AVPU score
 - Worsening of the respiratory condition as evidenced by
 - new requirement for bronchodilator or increased frequency of bronchodilator treatment.

Among children who had an induced sputum:

- Death within 4 hours following the procedure
- Clinical deterioration within 4 hours following the induced sputum procedure defined as:
 - Drop in oxygen saturation below 92%, resulting in increased supply of supplemental oxygen for 10 minutes or more
 - Deterioration in AVPU score
 - Worsening of the respiratory condition as evidenced by:
 - new requirement for bronchodilator or increased frequency of bronchodilator treatment.
- 5.7.2 Serious Adverse Event Reporting

All serious adverse events as defined above will be recorded at each site and reported to the PERCH Safety Monitor, DCC, PERCH PI, and the IRB. The SAEs will be graded by severity and by relatedness to the procedure.

This is a study of serious pneumonia in children and we do not plan to report every death to the JHSPH IRB, unless the death meets the definition of an SAE (section 5.7.1). The PERCH PI will, however, report to the IRB any deaths or other safety events which are considered to be serious and *related to study procedures* and unexpected. Non-serious adverse events will not be reported.

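### The desaturation SAE in section 5.7.1 is a crossing of 92% with no pre-procedure reference, so it does not say how a child already below 92% is counted

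*Protocol*

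**What the plan says.** Protocol section 5.7.1 lists, separately for lung aspirate and induced sputum, what makes clinical deterioration within 4 hours an SAE. The saturation item is the same in both lists: "Drop in oxygen saturation below 92%, resulting in increased supply of supplemental oxygen for 10 minutes or more". Beside it stand deterioration in AVPU score and a new or increased bronchodilator requirement. Death is also an SAE: within 4 hours for induced sputum, and at any time in the hospital stay for lung aspirate. The lung-aspirate list adds pneumothorax and haemoptysis above 5 mL.

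On who may have each procedure:

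- **Induced sputum.** Section 4.5.1.5 gives as a contraindication "severe hypoxia (<92% on supplemental oxygen", and section 5.2 repeats it as "oxygen saturation of less than 92% on oxygen". A footnote to Table V adds: "Delay collection of induced sputum from those with bronchospasm and severe hypoxia until clinical conditions permit".
- **Lung aspirate.** Sections 4.5.1.4 and 5.1 give no saturation value. The nearest item in section 5.1 reads "patient is clinically unstable as determined by a clinician, CPR performed within the last 24 hours".

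On reporting, section 5.6 limits what is recorded after induced sputum to events meeting the section 5.7 definition. It also provides for other events that are serious, related and unexpected. Section 5.7.2 sends monthly cumulative SAE reports to the Safety Monitor and leaves the study PI to decide from the safety reports whether the procedures continue.

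**The concern.** A criterion fixed at one absolute value works only for children who start on the other side of it. A child who goes from 93% to 91% and has oxygen increased for 10 minutes meets it. A child who goes from 90% to 78% and has oxygen increased for an hour does not, if a drop below 92% means passing from above that value to below it. The larger deterioration, in the child with less reserve, would be the one left out.

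Section 5.2 itself names a raised oxygen requirement lasting minutes to hours as a possible effect of induced sputum, so this is a harm the SAE list is meant to pick up. If the count is incomplete for children with a low starting saturation, the Safety Monitor and the study PI judge the procedures on an incomplete count.

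**Working it through.** The protocol states no figure for this point and none can be derived, so no arithmetic applies. The check sets the SAE wording against the rules for each procedure and then against the other reporting routes.

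**Step 1: which children can have the procedure, and can they meet the saturation criterion as worded?**

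| Procedure | Saturation before the procedure | Excluded by a stated saturation rule? | Can the criterion be met on a literal reading? |
|---|---|---|---|
| Induced sputum | 92% or above, with or without oxygen | No | Yes |
| Induced sputum | Below 92% on oxygen | Yes (4.5.1.5, 5.2) | Does not arise while the contraindication lasts |
| Induced sputum | Below 92% on room air | No, as worded | No |
| Lung aspirate | 92% or above | No | Yes |
| Lung aspirate | Below 92%, on oxygen or not | No; only a clinician's judgment of instability | No |

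Two rows leave a gap. The induced-sputum row is possible because section 4.5.2 asks for saturation on room air whenever this can be done. The Table V footnote on delaying collection does not clearly close it, because section 4.5.1.5 explains severe hypoxia as a reading below 92% on supplemental oxygen.

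**Step 2: in those two rows, what else would make the event an SAE?**

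- AVPU deterioration, bronchodilator need and death apply whatever the starting saturation. For lung aspirate, so do pneumothorax and haemoptysis.
- The remaining event is an isolated further fall in saturation that needs more oxygen, with none of these.

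**Step 3: would that isolated event be reported by another route?**

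- The general route in section 5.6 needs an event that is serious, related and unexpected. Section 5.2 already describes a raised oxygen requirement after induced sputum, so that event is hard to call unexpected.
- After induced sputum, section 5.6 records only events meeting the SAE definition, and section 5.7.2 does not report non-serious events.
- Section 5.6 does say that clinical measures before, during and after the procedure are tracked and reported to the coordinating institution's IRB. These measures are not described as part of the monthly SAE report.

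On the literal reading, the isolated event can therefore fail to reach the SAE count that informs the decision in section 5.7.2.

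**The case against.** **The 92% figures match for induced sputum.** The contraindication uses the same value as the SAE, and section 4.6 expects induced sputum to be missing in the sickest children. This stands. Induced sputum is done in most cases, and the children who are most hypoxic on oxygen do not have it while that lasts. Only the room-air reading remains.

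**Lung aspirate is uncommon.** Section 4.2.4 names four sites and says only a minority of cases have suitable consolidation. Unstable children are excluded, and the SAE list is longer. This stands as a limit on size. It does not supply a saturation rule.

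**The wording can be read differently.** A drop below 92% can mean a fall that ends under 92%, in which case 90% to 78% with more oxygen counts. This is a fair reading, but the text does not choose it. Seven sites could apply two readings to the same event, so a clarifying line is needed either way.

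**The criteria were settled with the IRB, and SAEs are graded.** The change log records corrections made after IRB correspondence, and section 5.7.2 grades events by severity and relatedness. Grading helps with trivial events that are counted. It does nothing for events that never enter the count.

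A reader might go further on altitude, because Table IV describes oxygen saturation as "continuous scale (oximetry), adjusted for altitude", and infer that an unadjusted 92% contradicts it. The documents do not support that. Table IV lists variables that may be evaluated at admission and places no requirement on the SAE threshold. The oximetry method in section 4.5.2 and the induced-sputum contraindications carry no adjustment either.

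**Conclusion.** The point holds in a limited form. The saturation criterion has no pre-procedure reference. On its ordinary reading it misses an isolated further desaturation needing more oxygen in a child already below 92%. This can arise at lung aspirate, where no saturation value excludes such a child, and more narrowly at induced sputum in a child below 92% on room air. The conclusion rests on reading the criterion as a crossing of 92%; on the other reading the defect is ambiguity between sites.

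Two stronger inferences are not supported. One is that safety monitoring cannot see deterioration in hypoxic children: the AVPU, bronchodilator and death criteria still apply, and section 5.6 requires monitoring around the procedure. The other is a number of affected children obtained by applying an assumed share to the 6300 target cases. The protocol gives no such share, and many of those cases would have neither procedure or would be barred from induced sputum. The size cannot be derived from the document.

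The change is worth making because it alters which events reach the people who decide whether the procedures continue.

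**What to change.** Reconcile section 5.7.1 with the lung-aspirate contraindications (4.5.1.4, 5.1) and the induced-sputum contraindications (4.5.1.5, 5.2) on how a low starting saturation is counted:

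1. Record on the SAE form the saturation immediately before the procedure and the oxygen flow at that time.
2. Keep the present criterion for children who start at 92% or above.
3. State in section 5.7.1, for both procedures, that where the pre-procedure value is already below 92%, a further fall from it that leads to increased oxygen for 10 minutes or more is counted as the event.

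This is a counting and reporting rule. It does not alter who has a procedure or how a child is managed. The cost is a line of text and a form field, since section 5.6 already requires monitoring before the procedure. The small downside is somewhat more reported SAEs, some of them minor. The existing oxygen condition and the grading in section 5.7.2 limit that.

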5.8 Study PI role in safety assessment and reporting

The PERCH study PI will hold overall responsibility for the safe conduct of the study. This will be achieved through several mechanisms. All study procedures will be implemented by the Site PIs according to the study Standard Operating Procedures. It is the responsibility of the Site PI to assure adherence to the SOPs, training of local personnel, and corrective action for deviations from the SOPs. Site PIs will report to the PERCH Study PI when significant deviations from the SOPs occur which might incur risk to study participants. The PERCH-independent external Safety Monitor will report directly to the PERCH Study PI as well as to the Site PI relevant to the safety event. The PERCH Study PI and or the Site PI has the authority to pause any or all PERCH study activities at a clinical field site if there are safety concerns. The PERCH Study PI will report to the Johns Hopkins IRB and to each Study Field Site PIs on all related and unanticipated SAEs received. Field Site PIs will report these to their own IRBs if required by the procedures and regulations established at the site.

5.9 DCC role in safety assessment and reporting

The DCC will be responsible for receiving initial SAE reports and updating the initial reports to create final reports. The DCC will be responsible for reporting the initial SAE to the PERCH Safety Monitor, the PERCH PI and the Site PIs. The DCC will also be responsible for compiling cumulative monthly SAE reports and disseminating them to the PERCH PI, PERCH Safety Monitor and the Site PIs.

5.10 Role of PERCH Core Team in safety assessment and reporting

The PERCH Core Team at JHSPH will serve as a 'study coordinating center' and support the responsibilities of the PERCH PI in safety assessment and reporting. The PERCH Core Team will receive all reports from the PERCH Safety Monitors on behalf of the PERCH PI, assure that these are assessed by the PERCH PI or his designee within 48 hours of receiving the report and will be responsible for providing reports to the Johns Hopkins IRB. In addition staff from the PERCH Core Team will report to the PERCH Study PI and to the relevant Field Site PI any safety concerns observed during site visits.

6 Statistical considerations

6.1 Overview

The overarching goal of PERCH is to describe the distribution of pathogens causing severe and very severe pneumonia in children around the developing world. This information will be useful for determining new treatment algorithms and for prioritizing development of new diagnostics, treatments, and vaccines.

To achieve its goal, PERCH is collecting multiple specimens from patients with pneumonia and controls and testing them thoroughly with highly sensitive detection methods. Equally important to this goal, PERCH is developing a statistical analysis and data interpretation approach that will use this information to accurately describe the pathogens associated with pneumonia. Specifically, the PERCH approach to statistical analysis will estimate (1) the prevalence of infection for each of approximately 30 specific pathogens among cases of hospitalized severe pneumonia and (2) the frequency of each of these pathogens as a putative cause of hospitalized, severe pneumonia. It will also accurately estimate the proportion of cases with no pathogen identified. This "unknown" group will be a high priority for pathogen discovery efforts.

[figure not shown]
6.2 Analysis plan for each objective

6.2.1 Determine the association between pneumonia and infection with known putative viral, bacterial, mycobacterial and fungal pathogens

The basic structure of the analytic problem is pictured in Figure 5 below. There are a set of risk factors or other attributes (denoted "X") of children that influence the risk of being infected (denoted "I") with a given pathogen. We cannot know in truth whether children are truly infected, but we infer this based on a series of laboratory measurements ("M") which include among others, for example, multiplex PCR of nasal secretions, culture of blood for bacterial pathogens, and assessment of induced sputum for acid fast bacilli. Among the infections children have, only some of these pathogens are causally linked to their disease, namely hospitalized, severe pneumonia (denoted as "Y").

[Note: For the sake of simplicity we will use "30" pathogens as an example of how many different individual pathogens we will identify in PERCH and we use "40" as an example of how many lab measurements there are. These numbers are approximations of the number of pathogens that can be identified or the number of lab measurements being collected, and are merely place holders for the sake of clarity. Also, one of the "pathogens" is the "no pathogen identified" category that is relevant to future pathogen discovery efforts.]

Figure VII. Basic structure of the measurement of and relationship between infection and disease in cases

PERCH Protocol

The key features of this formulation of the epidemiologic problem include the following:

[figure not shown]
- Infection status is a binary indicator for each of the 30 pathogens that can be measured, plus one additional broad category that includes "all others that are not identified by the lab testing". As there are 31 binary indicators of infection status for each child, there are 2³¹ (i.e., over 2 billion) possible infection states (i.e. infected or not infected for each of 31 "pathogens"). This enormous number of possible infection states, most of which have 0 people in them, creates statistical and modeling complexity which must be addressed. Below we discuss ways of reducing this dimension by smoothing (aggregating) across the "neighboring" cells to make estimation feasible.
- 2. Risk factors for infection with a given pathogen, including among other variables age, vaccination status, socioeconomic status, nutritional status, HIV infection, and antibiotic use are allowed to affect the risk of having each of the 30+1 infections. Some of these risk factors may also affect the general probability of developing 'hospitalized pneumonia' by a pathway other than the specific infection, for example, by reducing access to medical care.
- 3. Hospitalized, severe pneumonia is caused by one or more of the 30+1 pathogens causing infection and possibly by two-way interactions between them.
- We do not directly observe the presence of each infection. Rather the presence of infection by each pathogen must be inferred from up to 40 laboratory test results ("M") (illustrated in Table XII).

Table XII. Determination of infection status for30 pathogens using results from 40 lab tests						
Path 1 Path 2 Path 30						
Lab test 1	infected	NA	NA			
Lab test 2	NA	infected				
Lab test 40	Infected	Infected	NA			

5. The sensitivity and specificity of each laboratory test will be represented by a distribution on (0,1) (i.e., estimates of sensitivity and specificity can range from >0% up to and including 100%). Information from existing literature on the laboratory assays will be used to estimate their sensitivity and specificity. Uncertainty bounds around the sensitivity and specificity measures of the lab tests will be incorporated.

Data analysis ignoring measurement error. If the infection status for each of the 30 pathogens was known for each pneumonia case and for controls, the approach to analysis would have two parts, denoted A, in red, and B, in green, in Figure 6 below.

Figure VIII. Analysis approach

In Part A, among the cases and among the controls we will regress the presence/absence of infection for each pathogen on risk factors. The co-occurrence of infections would be of particular interest. We will therefore estimate the pairwise odds ratio for each of the 30 choose 2 = 435 pairs of infections, focusing on a smaller subset (e.g. top 30) with substantial prevalence. *Using marginal models* (e.g. Diggle, Heagerty, Liang and Zeger, 2002), the odds ratios could be regressed on covariates to build an understanding of what factors (e.g. age, nutritional status, vaccination status) influence the co-occurrence of pairs of infections (Diggle PJ 2002).

The analysis of Part A would permit construction of the histogram (or pie chart) of the frequency of pathogens, separately for cases and for controls, for any given set of risk factor values.

In Part B, using the cases and the controls we will regress the presence/absence of pneumonia on the indicators of infection and on selected interactions. Each coefficient represents the contribution of that infection (or pair of infections) on the risk of pneumonia. Given the large number of predictors relative to the expected number of pneumonia cases, *we propose to use the LASSO approach* to select a smaller subset of main effects and interactions that best predict case status (i.e. hospitalized pneumonia) (R 1996; Park 2007).

Because the analysis of Part B will be done with case-control data, only the relative odds of pneumonia for each pathogen-specific infection can be estimated. Specifically, we will be estimating for each pathogen and for various co-pathogen pairs the likelihood of infection given that the child has pneumonia compared with the likelihood of infection given that the child does not have pneumonia. Odds ratios that are near or approaching one are interpreted therefore to mean that there was a near equal likelihood of infection among the cases and the controls and no specific evidence that the pathogen was causally associated with pneumonia status.

The lack of association does not mean that the pathogen does not cause pneumonia; it simply means that there is no evidence of a causal association using measurement "M". In other words we are not assessing the relative *risk* of pneumonia given infection, we are only assessing the relative *likelihood* (or odds) of infection given pneumonia status compared with the likelihood of infection given control status. These relative odds values will be applied to the infection prevalences in the first histogram to obtain the histogram of causal effects, given covariates. The LASSO procedure will tend to shrink most regression coefficients in Part B towards 0. This will give the corresponding infections 0 as their estimated causal effect. If this is unsatisfactory, we will use alternatives to the LASSO that shrink less.

Pneumonia must be caused by a pathogen (or other exposure), although not necessarily by the ones in our list of 30. In cross-sectional study designs, the absolute prevalence of "other" pathogens (which could include, for example, toxic environmental exposures or as yet undiscovered pathogens) would be estimated by the intercept in the logistic regression in Part B. However, with the proposed case-control study design, an auxiliary source of information about hospitalized pneumonia case prevalence will be required to estimate the absolute prevalence of pathogen specific pneumonia episodes (i.e., going from percent of enrolled study cases with a given pathogen to prevalence in all community cases of a given pathogen).

Dimension reduction: A challenge of this study is the large number of infections that can be observed. One way to address this problem is to assume that there are a small number of "classes" of children and that the infection profile can be approximated by a common prevalence histogram within each class. The classes and infection prevalences can then be

estimated using a *latent class model* (Goodman 1974). One extension that allows each child's profile to vary in a space defined by the latent class profiles is *the grade of membership model* (e.g. Erosheva, 2003)(J. M. Bernardo 2003). We will explore these and other dimension reduction methods as needed.

We have explored the use of the latent class model approach and recognize at the outset some limitations. Primarily the assumption of independence of observations (i.e. lab measurements) that form the data inputs is violated in the data of the PERCH study. For example, an NP specimen from a child will be tested for multiple pathogens using a multiplex PCR approach. Anything that impairs the sample (e.g. poor handling of the sample) will uniformly affect the lab results from this sample for a wide range of pathogens, thus they will all be negative. A second problem with LCA is that the classes cannot be defined *a priori*, but instead are defined by the model output itself. As a result we will not have pathogen by pathogen etiologic proportions, which is the desired primary goal for the PERCH analysis.

Measurement error: The main challenge is that infection status will not be observed exactly for any child. Rather a series of laboratory test results will provide noisy evidence about each infection. For each test, there will be some degree of prior knowledge about its sensitivity and specificity. *A measurement error model* will be included in the analysis as represented by Part C in Figure 6 above.

We will consider two approaches for incorporating measurement error. In the first we will assume that the lab test results are independent of one another. We will use the external knowledge about sensitivity and specificity to set prior distributions for each. The joint probability distribution of the unknown infection status of a child will be inferred from the test results given the child's values of X and Y. We will only infer the univariate and bivariate marginal distributions. It will be possible to infer the class probabilities in the latent class version.

This approach ignores the likely correlation among test results that use the same body fluid or extraction process. We will extend the independence model by allowing for fluid and extraction "errors" that cause all of their test results to be corrupted (usually toward zero).

Approach to analysis: Once the measurement error is acknowledged, analysis will be implemented *using a Bayesian hierarchical model and Markov chain Monte Carlo (MCMC) methods of inference*. We will repeatedly simulate from the conditional distributions of the infection statuses (I) and the model parameters given the observable (X, Y, M). The histograms that are the target of inference will be constructed, with uncertainty, by summarizing the distribution of the I's and of the I's from the analysis. In the first months of the project, the detailed specification of the hierarchical model will be developed and tested on simulated data.

6.2.2 Estimate the fraction of pneumonia attributable to pathogens for which vaccines are currently under development

(See section 6.2.1. above).

